4.1 Inclusion/Exclusion Criteria

AS-Caregiver dyads are eligible for inclusion if the:

- Caregiver reports that the individual with AS has a laboratory-confirmed diagnosis of Angelman syndrome
- Individual with AS is at least 1 year old
- Caregiver is willing and able to provide informed consent for themselves and oversee study participation
- Caregiver or legal guardian is willing to provide informed consent on behalf of the individual with AS
- Caregiver is comfortable reading and speaking in English
- Caregiver has access to a smartphone or tablet that is compatible with the study app OR caregiver has internet access and is willing to use a wi-fi only device to record and upload videos

NT-Caregiver dyads will be eligible for inclusion if the:

- Neurotypical individual is between 1 and 8 years of age
- Caregiver is willing and able to provide informed consent and oversee study participation and NT individual is willing and able to provide assent, as applicable
- Caregiver is comfortable reading and speaking in English
- Caregiver has access to a smartphone or tablet that is compatible with the study app OR caregiver has internet access and is willing to use a wi-fi only device to record and upload videos

Participant-Caregiver dyads will be excluded from the study only if they do not meet the inclusion criteria above.

4.2 Recruitment

AS-caregiver dyads will be recruited for this study through referrals from collaborators and advocacy groups as well as through direct marketing via social media. Boston Children's Hospital's Department of Neurology (BCH) and advocacy groups will not be responsible for direct recruitment of the study participants. Rather, BCH and advocacy will facilitate recruitment by making available to interested caregivers Institutional Review Board (IRB) approved recruitment materials. If caregivers provide written or verbal consent to be contacted by Casimir study staff, BCH may share their contact information with Casimir study staff via a secure channel. Potential participants may also share their contact information directly with Casimir via a secure, online form.

Additionally, recruitment for the study may also occur through postings with patient advocacy groups and on social media. Casimir will supply the advocacy groups with IRB-approved language for website postings and group emails. All contact information will be obtained using a secure web form that is compliant with Health Insurance Portability and Accountability Act (HIPAA) and General Data Protection Regulation (GDPR).

4.3 Informed Consent

Casimir study staff will explain the study and answer any questions on an initial call. Casimir will obtain verbal consent prior to the official electronic consent (e-consent) process that takes place. If interested, Casimir study staff will conduct e-consent/assent using the following process:

- Casimir study staff will schedule a phone call/web-conference with potential participant-caregiver dyads and send the informed consent form (ICF) and any applicable assents.
- Casimir staff will review the ICF and any applicable assents with the potential participant-caregiver dyad.
- Casimir study staff will provide the potential participant and caregiver with the opportunity to ask questions.
- If the participant and caregiver verbally consents/assents during the phone call/webconference, Casimir study staff send the appropriate ICF and/or assent forms to participants to be signed electronically using a web-based signatory system and in accordance with applicable Casimir Standard Operating Procedure and applicable study specific plans and/or Work Instructions

If the caregiver in a participant-caregiver dyad is unable to legally provide informed consent for the participant, a legal guardian of the participant who can provide consent will also be included in the consent process described above.

Copies of the signed informed consent and any applicable assent form will be provided to the caregiver and/or legal guardian once signatures are completed. Study staff will also maintain a copy of the electronically signed consent and applicable assent form. Appropriate IRB-approved informed consent and/or assent forms will be used based on the age and mental capacity of the participant.

4.4 Eligibility Determination

Eligibility will be established if the potential participant-caregiver dyad meets all the inclusion criteria.

4.5 Discontinuation Criteria

Casimir, in coordination with the funder, Ionis, may elect to discontinue this study at their discretion. Participant-caregiver dyads may elect to withdraw from the study at any time.

5 Study Procedures

5.1 Schedule of Visits & Assessments

Following informed consent and during the baseline period, caregivers will participate in a remote administration of the Vineland Adaptive Behavior Scales (VABS-3) conducted as an interview. After the Baseline VABS-3, a Training Call will be scheduled by phone or secure web conference to train participating caregivers for video capture and orient them to the study supply kit. After the Training Call, caregivers will capture Baseline ASVA videos, which includes capturing 2 sets of videos (baseline and retest captures). Approximately 12 weeks later, VABS-3 will be remotely administered again, and the participant-caregiver dyad will capture an additional set of ASVA videos and complete CGIC in the study app before exiting the study.

5.1.1 Baseline Visit Window

The baseline visit window may span approximately 5 weeks. Caregivers will have approximately 2 weeks to complete the baseline VABS-3. Then, participant-caregiver dyads will have approximately 3 subsequent weeks to complete the Baseline Video capture. Visit windows may be extended at the discretion of the investigator.

5.1.2 12-Week Visit

Approximately 12 weeks after the baseline VABS-3 was administered, the 12-week visit window will open and may span approximately 4 weeks. The 12-week interview will be conducted during the first 2 weeks of the window after which participant-caregiver dyads will have approximately 2 additional weeks to complete the final video capture. Visit windows may be extended at the discretion of the investigator.

The table below summarizes the data to be collected at each visit.

Data to be	Data Captured at Remote Visits^		
Collected/Assessments	Consent Call	Baseline	12 Weeks Visit
Contact Information (PII)	Х		
Demographics & Medical History (PHI)	Х		
ASVA		X*	X**

Data to be	Data Captured at Remote Visits^		
Collected/Assessments	Consent Call	Baseline	12 Weeks Visit
VABS-3		Х	X
CGIC			Х

^{*}Baseline ASVA will be captured twice (test-retest) over a 3-week window.

PII=Personal Identifiable Information; PHI=Protected Health Information; ASVA=Angelman Syndrome Video Assessment; VABS-3 = Vineland Adaptive Behavior Scales v3; CGIC = Caregiver Impression of Change

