Key Inclusion/Exclusion Criteria:	AS-caregiver dyads will be enrolled if the caregiver reports a laboratory confirmed diagnosis of AS, the participating individual with AS is at least 1 years old, and the caregiver is comfortable reading and speaking English. NT-caregiver dyads will be enrolled if the child is between 1 and 8 years old and the caregiver is comfortable reading and speaking English.
Schedule of Assessments:	ASVA videos will be captured 3 times (baseline, baseline re-test, and at a 12-week visit). VABS-3 will be administered 2 times (baseline and at a 12-week visit) as an interview with caregivers. CGIC will be captured in the study app for each of 4 domains at the 12-week visit.
Data Analysis:	Videos will be reviewed and analyzed to develop an ASVA scoring/rating system. Videos captured of neurotypical children will be used as a qualitative comparator to ensure the ASVA scoring system is sufficiently specific to physical and behavioral manifestations of AS. VABS-3 and CGIC data will be used as comparators for validation analyses of ASVA.

2 Introduction & Background

Angelman syndrome (AS) was first described in 1965 as a neurodevelopmental disorder characterized by global developmental delay leading to severe intellectual disability, lack of expressive language, ataxia, tremors, unique behavioral features including a happy predisposition, easy laughter, mouthing of objects, fascination with water, as well as maladaptive behaviors such as hair-pulling and other aggressive behaviors. It was subsequently found to be caused by a lack of expression of the *UBE3A* gene, which may be due to a deletion of the critical segment from the maternally-inherited copy of chromosome 15q11q13 that encompasses *UBE3A* (in about 70 - 75% of affected individuals), a pathogenic variant in the maternally-inherited copy of *UBE3A* (in about 10%), paternal uniparental disomy (UPD) of chromosome 15 (in about 5 - 10%), or an imprinting defect (in about 5 - 10%) Estimates of prevalence are approximately 1 in 20,000 to 1 in $50,000.^{1-3}$

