5.2.3 ASVA

Caregivers will capture videos of the participant doing activities in the home using a smartphone or tablet. All videos will be submitted via a HIPAA- and GDPR-compliant smartphone/tablet application (study app).

All activities are similar to usual behaviors for individuals with AS and NT children, like looking at a book, communicating yes or no, and walking or crawling. Activities were designed to capture the following relevant functional domains:

- Gross motor function
- Fine motor function
- Communication/Cognition
- Activities of daily living

^{**}Participant-caregiver dyads will have approximately 2 weeks after completion of the VABS-3 to complete the video submissions for ASVA (12-week visit)

[^]No data is collected at the Training Call.

Caregivers will be provided instructions and training for setting up, performing, and submitting the ASVA videos in an IRB-approved Video Capture Manual and through training videos that can be viewed in-app.

Depending on the functional ability of the participant, participant-caregiver dyads will capture and submit between 11 and 14 different activities. Caregivers have the option to skip any assigned activities. Videos will vary in length between 30 s to about 5 min in duration.

At baseline, participant-caregiver dyads will have 3 weeks to capture each assigned ASVA video twice (baseline and re-test). Once the first capture of a task is submitted and approved, caregivers will have the ability to collect the re-test capture of that same activity. Caregivers may collect activity videos in any order during the baseline period as long as 2 captures of each task are completed.

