5.2.5 Caregiver Impression of Change (CGIC)

Caregivers will be asked to answer 4 questions in the study app after they have completed the final video capture for the 12-week visit. Caregivers will rate their impression of change during the study for each of the 4 functional domains captured by ASVA. They will rate change using IRB-approved questions on a 5-point Likert scale ranging from 1 = much worse to 5 = much better, with 3 = no change.

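### Do Sections 5.1 and 5.1.2 of the protocol time the 12-week visit from different events, and does that damage the comparisons of change?

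*Protocol*

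**What the plan says.** Section 5.1 of the protocol gives the order of events: baseline VABS-3 interview, Training Call, then the videos. On the videos it says "After the Training Call, caregivers will capture Baseline ASVA videos, which includes capturing 2 sets of videos (baseline and retest captures". The next sentence begins the follow-up: "Approximately 12 weeks later, VABS-3 will be remotely administered again, and the participant-caregiver dyad will capture an additional set of ASVA videos".

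Sections 5.1.1 and 5.1.2 supply the windows. The baseline VABS-3 has about 2 weeks. For the videos, "Then, participant-caregiver dyads will have approximately 3 subsequent weeks to complete the Baseline Video capture", and the whole baseline window is about 5 weeks. For follow-up, "Approximately 12 weeks after the baseline VABS-3 was administered, the 12-week visit window will open and may span approximately 4 weeks"; the interview falls in the first 2 weeks of that window. The footnote to the schedule table ties the last videos to that interview: "Participant-caregiver dyads will have approximately 2 weeks after completion of the VABS-3 to complete the video submissions for ASVA (12-week visit". All windows may be extended by the investigator.

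The CGIC (Section 5.2.5) is answered after the final video: "Caregivers will rate their impression of change during the study". The synopsis gives the purpose: "VABS-3 and CGIC data will be used as comparators for validation analyses of ASVA". Section 7 says the validation analyses cannot yet be defined, describes them in general as relating ASVA scores to VABS scores, and leaves the details to a SAP.

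**The concern.** Read in order, Section 5.1 counts the 12 weeks from the event just described, the baseline videos. Section 5.1.2 counts them from the baseline VABS-3, which comes before the Training Call and all videos. Two coordinators following the two sections could open the same dyad's visit on dates up to about 3 weeks apart, or 5 if the lag can fill the whole baseline window.

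What could suffer is any comparison of change. The CGIC records change only, so using it as a comparator needs an ASVA change over a known interval. If the ASVA and VABS-3 intervals differ within a dyad, their changes do not cover the same time. If the caregiver's starting point is unknown, the CGIC may cover a third interval. Interval differences can be handled later from recorded dates, but a caregiver's unstated reference point cannot be recovered once the question has been answered.

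**Working it through.** The protocol has no sample-size or power figure to reproduce here. The check is interval arithmetic on its windows, in weeks, with the baseline VABS-3 at 0 and before any extension.

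**Inputs**
- b, lag of the baseline video: 0 to 3 (Section 5.1.1), or 0 to 5 if it can fill the baseline window.
- o, follow-up interview after the window opens: 0 to 2 (Section 5.1.2).
- f, final video after that interview: 0 to 2 (Section 5.1.2 and the table footnote).
- Assumptions not in the protocol: b, o and f are independent and uniform, and each dyad has one baseline video date.

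**Step 1: do the two openings conflict?** Counting from the videos, the visit opens at 12 + b, which is week 12 to 15. The Section 5.1.2 window is week 12 to 12 + 4 = 16, so every such opening lies inside it. For b up to 2 the opening also lies inside the interview part, weeks 12 to 14. With b up to 5 the opening runs to week 17, one week beyond. The close does move: a full 4-week window opened at week 15 ends at 19 rather than 16.

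**Step 2: intervals under each anchor**

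| Anchor | VABS-3 interval | ASVA interval |
|---|---|---|
| Baseline VABS-3 | 12 + o = 12 to 14 | 12 + o + f - b = 9 to 16 (7 to 16 if b reaches 5) |
| Baseline videos | 12 + b + o = 12 to 17 (12 to 19) | 12 + o + f = 12 to 16 |

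**Step 3: the mismatch within a dyad.** ASVA interval minus VABS-3 interval:
- VABS-3 anchor: (12 + o + f - b) - (12 + o) = f - b.
- Video anchor: (12 + o + f) - (12 + b + o) = f - b.

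The anchor cancels. The gap is -3 to +2 weeks (-5 to +2 if b reaches 5), with mean 1 - 1.5 = -0.5 and SD sqrt(4/12 + 9/12) = 1.04. It exceeds 1 week in either direction with probability (0.5 + 2)/6 = 0.417, and 2 weeks with probability 0.5/6 = 0.083. Harmonising the two sections leaves all of these figures as they are.

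**Step 4: effect on a correlation of changes.** Let both measures change at the same personal rate r, with mean k and SD 1, so the changes are r·tA (ASVA) and r·tV (VABS-3) and the true correlation of rates is 1. Then

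corr = [(k²+1)·E(tA·tV) - k²·E(tA)·E(tV)] / sqrt{[(k²+1)·E(tA²) - k²·E(tA)²]·[(k²+1)·E(tV²) - k²·E(tV)²]}.

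VABS-3 anchor, b from 0 to 3: E(tA) = 12.5, var(tA) = 4/12 + 4/12 + 9/12 = 1.417, E(tV) = 13, var(tV) = 0.333, covariance 0.333.
- k = 0: 162.833 / sqrt(157.667 × 169.333) = 0.997.
- k = 2: (5 × 162.833 - 4 × 162.5) / sqrt(163.333 × 170.667) = 164.167 / 166.960 = 0.983.

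Simulation under the video anchor gives 0.997 and 0.987. At k = 2 the choice of anchor is therefore worth 0.004. With b uniform on 0 to 5 the values are 0.991 and 0.958 (VABS-3 anchor) and 0.995 and 0.975 (video anchor). With change reliability of 0.5, the simulated correlation is 0.50 to 0.60, against 0.50 for equal 12-week intervals, so nothing is lost.

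**Step 5: the CGIC.** Under Section 5.1.2 the span to the final video is 9 to 16 weeks from the baseline videos, 12 to 16 from the baseline interview, and 12 to 2 + 16 = 18 from consent, if the first window opens at consent. These spans overlap heavily. Section 5.2.5 describes the questions as approved by the IRB but does not print them.

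**The case for a change.** The best case for a change is that visit timing and a questionnaire's recall period govern data collection, so a later SAP cannot repair them. On its plain reading Section 5.1 does give a different anchor, the correction costs a few words, and validation is part of the study's objective. Extensions have no stated limit, so the real spread may exceed the figures above. In the worst case within the windows, an ASVA interval of 9 weeks sits beside a VABS-3 interval of 12, which is 3/12 = 25% shorter.

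Part of this stands. The wording of Section 5.1 is loose, and a cross-reference to Section 5.1.2 would be harmless. But the obvious way to reconcile the sections is to keep the Section 5.1.2 rule, and that alters no visit. The 9-against-12 case arises under the Section 5.1.2 rule itself, from the time allowed for filming. It is a fair trade-off for home capture of 11 to 14 activities, each filmed twice in any order. Because a domain score draws on several filming dates, the single-date model probably overstates the spread.

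The CGIC argument has force only if the questions themselves omit a starting point. The protocol does not show them, and its description does give a period. Using actual dates in any change analysis is ordinary SAP content, and Section 7 defers to a SAP.

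**Conclusion.** No change to the plan is needed. The difference between Sections 5.1 and 5.1.2 is a clerical looseness: an overview sentence with no named anchor beside an explicit rule that staff can follow. On the 0-to-3-week lag, the visit opening implied by the overview always falls inside the Section 5.1.2 window. The mismatch between ASVA and VABS-3 intervals (SD about 1 week) comes from the capture windows and is identical under either anchor, so reconciling the text gains nothing analytically. Its cost is small: a perfect correlation falls to 0.983 to 0.997 under the VABS-3 anchor, and to 0.958 at worst with a lag of up to 5 weeks.

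These figures assume uniform dates, linear change with mean rate 0 to 2 between-person SDs, and no extensions. The protocol gives no rate of change, and the study has no treatment and no fixed test of change. The unnamed CGIC start is a missing detail that the question text, not reproduced in the protocol, may already supply.

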5.2 Description of Remote Visits & Assessments

5.2.1 Consent Call

Study Coordinators will conduct e-consent via phone or web-conferencing platform. After consent is obtained, the caregiver's shipping address and other contact information will be confirmed. Study coordinators will also ask the caregiver for demographics and medical history information about the participant. The participant-caregiver dyad will then be sent a study kit of supplies needed to perform the at-home assessments. Study kits will be shipped to the caregivers in accordance with Casimir Standard Operating Procedures (SOPs). The contents of the study kit will be explicitly outlined in the Caregiver Manual and approved by the IRB.

5.2.1.1 Demographics & Medical History

For each participant, name, age, and sex will be obtained. For individuals with AS, caregivers will also be asked to report the participant's age at diagnosis and to report the mutation/deletion type of the participant's diagnosis.

5.2.2 Training Call

Once participants have received their study supply kit, a Training Call (approximately 1h duration) will be conducted via telephone or web-conference platform. Participants will be helped with download, registration, and use of the smartphone/tablet application (study app), and the Study Coordinator will orient the participant to the assessment materials and study kit.

5.2.3 ASVA

Caregivers will capture videos of the participant doing activities in the home using a smartphone or tablet. All videos will be submitted via a HIPAA- and GDPR-compliant smartphone/tablet application (study app).

All activities are similar to usual behaviors for individuals with AS and NT children, like looking at a book, communicating yes or no, and walking or crawling. Activities were designed to capture the following relevant functional domains:

- Gross motor function
- Fine motor function
- Communication/Cognition
- Activities of daily living

^{**}Participant-caregiver dyads will have approximately 2 weeks after completion of the VABS-3 to complete the video submissions for ASVA (12-week visit)

[^]No data is collected at the Training Call.

Caregivers will be provided instructions and training for setting up, performing, and submitting the ASVA videos in an IRB-approved Video Capture Manual and through training videos that can be viewed in-app.

Depending on the functional ability of the participant, participant-caregiver dyads will capture and submit between 11 and 14 different activities. Caregivers have the option to skip any assigned activities. Videos will vary in length between 30 s to about 5 min in duration.

At baseline, participant-caregiver dyads will have 3 weeks to capture each assigned ASVA video twice (baseline and re-test). Once the first capture of a task is submitted and approved, caregivers will have the ability to collect the re-test capture of that same activity. Caregivers may collect activity videos in any order during the baseline period as long as 2 captures of each task are completed.

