5.2.3.1 Video Re-shoots

Caregivers may be asked to re-record videos if Casimir study staff determine that the quality of the video is compromised.

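### The re-test of a task opens as soon as the first capture is approved, so the rule permits same-day test-retest pairs

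*Protocol*

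**What the plan says.** Section 5.1 has caregivers film the baseline ASVA after the Training Call, "which includes capturing 2 sets of videos (baseline and retest captures"), and gives no interval between the two sets. The footnote to the schedule table, under section 5.1.2, names the purpose of the pair: "Baseline ASVA will be captured twice (test-retest) over a 3-week window".

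Section 5.2.3 carries the working rules. The upper limit is "At baseline, participant-caregiver dyads will have 3 weeks to capture each assigned ASVA video twice (baseline and re-test"). The re-test opens on approval: "Once the first capture of a task is submitted and approved, caregivers will have the ability to collect the re-test capture" of the same activity. Order is free: "Caregivers may collect activity videos in any order during the baseline period as long as 2 captures of each task are completed".

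Two further provisions affect timing. Section 5.1.1 adds "Visit windows may be extended at the discretion of the investigator", which can lengthen the gap but sets no lower limit. Section 5.2.3.1 adds "Caregivers may be asked to re-record videos if Casimir study staff determine that the quality of the video is compromised", which can delay acceptance of a first capture. Section 5.2.3 also says caregivers receive "instructions and training for setting up, performing, and submitting the ASVA videos in an IRB-approved Video Capture Manual" and in-app training videos. Those materials are not part of the document.

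**The concern.** A test-retest pair should show how much a score moves when the person has not changed. For a measure of habitual function at home, that includes movement from one day to the next. Two clips filmed on the same day share sleep, mood, health and setting, so day-to-day variation drops out of their difference and is counted as stable difference between people. Reliability then looks too high and measurement error too low. If there is no day-to-day variation, there is no bias.

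The protocol does not say how large that variation is. Its background section describes sleep problems, easy excitability, a tendency to hyperactivity and frequent epilepsy in this population, so some variation is a reasonable inference. The same section says ASVA is meant to measure change, and a change score has to be judged against error across days.

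The stakes are limited. Preliminary validation is part of the objective (section 3.1), but section 7 names no reliability statistic and describes validation in general terms as the relation of ASVA to VABS scores. Only the evidence on score stability is affected. That evidence depends on when the clips are filmed, which a later SAP cannot change.

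**Working it through.** **Step 1: the permitted gap.** The protocol gives no figure to reproduce, so the limits come from reading the rules together.

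| Rule | Source | Effect on the gap |
|---|---|---|
| Re-test opens on approval of the first capture | 5.2.3 | Lower limit is the approval time, which is not stated |
| Both captures within 3 weeks | 5.2.3; schedule table footnote | Upper limit about 21 days |
| Window may be extended | 5.1.1 | Upper limit can grow |
| Tasks in any order | 5.2.3 | Gap may differ by task and family |
| Re-shoot on quality grounds | 5.2.3.1 | May delay acceptance; sets no minimum gap |

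The gap can run from the same day, if approval is quick, to about 3 weeks or more. Between those limits the caregiver chooses.

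**Step 2: what same-day pairs do.** All variances here are assumptions, since the protocol gives none: person variance 1.0, error variance 0.2, day-state variance *v* from 0 to 0.3. Let *p* be the share of same-day pairs, also unknown. Day-states on different days are taken as independent.

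- Error variance from different-day pairs: 0.2 + *v*
- Error variance from the pooled pairs: 0.2 + (1 − *p*)*v*
- SEM ratio, pooled to different-day: √[(0.2 + (1 − *p*)*v*) / (0.2 + *v*)]
- Pooled ICC: (1 + *pv*) / (1.2 + *v*), an overstatement of *pv* / (1.2 + *v*)

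For *v* = 0.3 and *p* = 0.25, the SEM ratio is √(0.425 / 0.5) = 0.922 and the ICC is 1.075 / 1.5 = 0.717, against 1 / 1.5 = 0.667.

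| *v* | Different-day ICC | SEM ratio at *p* = 0.25 / 0.5 / 1 | Pooled ICC at *p* = 0.25 / 0.5 / 1 |
|---|---|---|---|
| 0 | 0.833 | 1.000 / 1.000 / 1.000 | 0.833 / 0.833 / 0.833 |
| 0.05 | 0.800 | 0.975 / 0.949 / 0.894 | 0.810 / 0.820 / 0.840 |
| 0.1 | 0.769 | 0.957 / 0.913 / 0.816 | 0.788 / 0.808 / 0.846 |
| 0.3 | 0.667 | 0.922 / 0.837 / 0.632 | 0.717 / 0.767 / 0.867 |

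The SEM is thus understated by 0-8%, 0-16% and 0-37% for the three shares, and the ICC overstated by 0-0.05, 0-0.10 and 0-0.20.

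**Step 3: whether an SAP can repair it.** If capture times are kept, an SAP could use only the different-day pairs. With two captures per person, a one-way model and normal errors, *n* pairs give *n* degrees of freedom for the error variance. The 95% CI for the SEM is the estimate times √(*n* / χ²₀.₉₇₅,ₙ) to √(*n* / χ²₀.₀₂₅,ₙ).

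| Different-day pairs for one task | 95% CI factors |
|---|---|
| 40 (all Angelman syndrome dyads) | 0.82-1.28 |
| 20 | 0.77-1.44 |
| 4 | 0.60-2.87 |

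These factors do not depend on the assumed variances. A model across tasks could be tighter. A task with only same-day pairs gives no such estimate: those pairs alone cannot separate day-state from person variance. The 12-week capture does supply a different day, but real change over 12 weeks is mixed in, so it is a partial cross-check.

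**The case against.** The strongest case against is that nothing in the text contradicts itself and that the approval gate already separates the two captures. If staff usually take a day or more, same-day pairs hardly occur. Spacing advice may be in the Video Capture Manual. Both points stand and bear on how often the problem arises. Neither removes it, because the protocol states no approval time and requires no spacing.

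It is also fair that no named analysis depends on the pair, that the variances are assumed, and that the 37% figure needs every pair to be same-day and a day-state variance 1.5 times the error variance (0.3 / 0.2). Those points limit the size claimed.

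A further point is that section 7 plans domain scores as well as activity scores. If the tasks of a domain are filmed on different days, the day-states partly average out. That lowers the ICC overstatement. It does not lower the proportional SEM understatement if the residual error averages out equally. If a family films a whole domain in one day, the shared day-state does not average out and the effect on the domain score is larger.

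A later-day rule is also imperfect, since an evening and the next morning may share an illness or a bad night. It would reduce the problem without guaranteeing independent days. Finally, a short gap limits real change in young children, and families have 11 to 14 activities to film twice, 22 to 28 clips. That argues against a long minimum; a next-day minimum is compatible with it.

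**Conclusion.** The concern holds. As written, the protocol allows test and re-test of a task on the same day and lets the gap vary by task and family up to the end of an extendable window.

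The consequence, if day-to-day variation exists, is overstated reliability and understated measurement error. Its size cannot be found from the document and may be zero. A mild case (day-state variance 0.05, a quarter of pairs same-day) understates the SEM by 2.5%, with an ICC of 0.81 against 0.80; the 37% figure is an upper bound within the assumed range. These figures rest on the assumed variances and on independent day-states.

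The change should be made, though the matter is not critical: the affected evidence is secondary to the analysis named in section 7, but different-day pairs that were not filmed cannot be recovered. Confidence is medium, because the approval time and the content of the capture manual are unknown.

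**What to change.** In section 5.2.3, state that the app opens the re-test of a task only after approval and only on a later calendar day than the recording of the accepted first capture. State also that the date and time of each capture are recorded, so that the reliability analysis can account for the actual gap. Any longer minimum or target range is for the sponsor to decide.

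The cost is one date check on an existing app gate and a short addition to the text. A re-test is delayed only when approval falls on the day of recording, and then only to the next day; when approval comes later there is no added wait. Caregivers must film on at least two days, and first captures must be done by about day 20 of the 21-day window (21 − 1 = 20). Some late or re-shot clips may need the extension that section 5.1.1 already allows; how many cannot be told from the document.
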